2. LIST OF ABBREVIATIONS

1L First line
2L Second line
3L Third line
AE Adverse Event

BI Boehringer Ingelheim

CDC Center for Disease Control and Prevention Center

CI Confidence Interval

CSCO Chinese Society of Clinical Oncology

CTN Clinical Trial Notification
DDLPS Dedifferentiated liposarcoma

ECOG Eastern Cooperative Oncology Group

ENCePP European Network of Centres for Pharmacoepidemiology and

Pharmacovigilance

FDA Food and Drug Administration

GCP Good Clinical Practice

GPP Good Pharmacoepidemiology Practice
GVP Good Pharmacovigilance Practices
HCRU Healthcare resource utilization
IEC Independent Ethics Committee

IQR Interquartile range

IRB Institutional Review Board

KM Kaplan-Meier LOT Line of therapy

MAH Marketing Authorization Holder MDM2 Mouse double minute 2 homolog

NATDSS National Anti-Tumor Drug Surveillance System

NCC National Cancer Center

NCCN National Comprehensive Cancer Network

NIS Non-Interventional Study

NIS-DMRP Non-interventional Study-Data Management and Review Plan

OS Overall survival

PASS Post-Authorization Safety Study

QC Quality control SD Standard deviation

SEAP Statistical and Epidemiological Analysis Plan SEER Surveillance, Epidemiology, and End Results

SOP Standard operating procedure

TP53 Tumor protein 53

NIS Protocol BI Study Number 1403-0024 Page 6 of 37 C42272174

Proprietary confidential information© 2023 Boehringer Ingelheim GmbH or one or more of its affiliated companies

4. ABSTRACT

NIS Protocol BI Study Number 1403-0024 Page 7 of 37 C42272174

Name of company:			-
Boehringer Ingelheim			
Name of finished me product: Not applicable	edicinal		
Name of active ingr Not applicable	edient:		
Protocol date:	Study number:	Version/Revision:	Version/Revision date:
31 May 2023	1403.0024	1.0	
Title of study:	 		
Rationale and background:	Demographic, clinical characteristics, and treatment outcomes associated with dedifferentiated liposarcoma patients in China Liposarcoma is a malignancy of fat tissue and is one of the most commonly occurring types of soft tissue sarcoma, a heterogeneous group of rare malignancies with over 150 different histological subtypes. In 2020, the World Health Organization, reclassified liposarcomas into the following distinct categories: atypical lipomatous tumor/well-differentiated liposarcoma; myxoid liposarcoma; pleomorphic liposarcoma; myxoid pleomorphic liposarcoma; and dedifferentiated liposarcoma (DDLPS), which represents 15-20% of all liposarcoma cases [R23-1182]. DDLPS is characterized by amplification of the mouse double minute 2 homolog (MDM2) gene. MDM2 is a negative regulator of tumor protein 53 (TP53) [P20-03237]. There are few published epidemiological studies of DDLPs with quite limited incidence and prevalence data. The mainstay of first line (1L) therapy for advanced DDLPS remains an anthracycline-based regimen despite its moderate efficacy in this setting (objective response rate <15%; median progression-free survival: 2 to 4 months; median overall survival (OS, from initiation of 1L treatment to death or end of study): 8 to 12 months) [R21-0720]. Notably, the natural history, patient journey and treatment outcomes of this rare disease is poorly understood in Chinese patients. Boehringer Ingelheim (BI) is currently developing BI 907828, an orally available MDM2-p53 antagonist, for treatment of DDLPS. On 22 August 2022, BI China received Clinical Trial Notification (CTN) for MDM2 DDLPS indication from China authority. In the CTN, China authority recommended BI to collect Chinese DDLPS patients' survival and other related clinical data in the real-world, to provide support for future analysis during New Drug Application. Therefore, we conduct this study to investigate the patient characteristics, current treatment patterns and outcomes in Chinese DDLPS patients.		

NIS Protocol BI Study Number 1403-0024 Page 8 of 37 C42272174

Research question	Drimary chicativa				
and objectives:	Primary objective:				
	 To describe the overall survival (OS) of Chinese unresectable locally advanced or metastatic DDLPS patients 				
	Secondary objectives:				
	To describe the treatment patterns of Chinese DDLPS patients				
	Exploratory objective:				
	To describe demographic, clinical characteristics and treatment				
	outcomes of Chinese DDLPS patients				
	To describe the direct medical cost and healthcare resource utilization of Chinese DDLPS patients				
Study design:	This will be a non-interventional/observational study of Chinese DDLPS				
	patients using existing data curated by Indiana. No Boehringer Ingelheim (BI) product will be studied, and no new interventions or procedures will be collected.				
	The proposed study period will be January 1, 2013 through December 31, 2022. Eligible patients will be identified from January 1, 2013 to December 31, 2021 (one year before end of study period). Patients will be followed from index date until death, end of study period, or loss to follow-up, whichever occurs first.				
Population:	Inclusion criteria:				
	 Patient has two or more documented clinical visits in the National Anti-Tumor Drug Surveillance System (NATDSS) network on or after January 1, 2013. 				
	Patient has a confirmed diagnosis of DDLPS during his/her lifetime.				
	At least 18 years old at the date of initial diagnosis				
	No exclusion criteria are applied.				
	Eligible population will be divided into two groups:				
	• Cohort 1 will include unresectable locally advanced or metastatic DDLPS patients who received at least one line of systemic antineoplastic treatment by the end of cohort identification period (index date = start date of 1L treatment).				
	• Cohort 2 will include patients with DDLPS who have not initiated 1L systemic antineoplastic treatment by the end of cohort identification period (index date = date of initial DDLPS diagnosis during cohort identification period). Patients initiated 1L treatment afterwards or patients received adjuvant and/or neoadjuvant therapy only through follow-up will be included in Cohort 2.				
Variables:	This analysis is descriptive, in that there is no a priori hypothesis being assessed. Thus, there are no pre-specified exposures or covariates that will be used as the basis for comparison a priori.				
	The primary outcome is OS. Secondary outcomes include survival after initial diagnosis, and treatment patterns. Exploratory outcomes may include patient demographics, clinical characteristics, duration of treatment, time to next treatment by lines, healthcare resource utilization and direct medical cost, etc.				

NIS Protocol BI Study Number 1403-0024 Page 9 of 37 C42272174

Proprietary confidential information© 2023 Boehringer Ingelheim GmbH or one or more of its affiliated companies

Data sources:	will develop a custom, curated dataset for this study based on longitudinal electronic medical records data from the National Anti-Tumor Drug Surveillance System (NATDSS), the largest cancer registry database in China. This database, established in 2018 by China National Cancer Center (NCC), covers over 1400 hospitals across 31 provinces and over 10 million cancer patients in China. This multicenter hospital-based database consists of data of 1509 variables from 7 aspects including drug, patient basic information, inpatient, outpatient, medical technology, treatment and follow up. NATDSS is linked with National Mortality Database from Chinese Center for Disease Control and Prevention Center (China CDC) to obtain patients' death information.
Study size:	The patient sample will be a convenience population of all eligible patients in the database who met inclusion and exclusion criteria during the study period; no priori power analyses were conducted.
Data analysis:	This study will be descriptive in nature. Continuous variables will be summarized using mean, standard deviation (SD), median and range. Categorical measures will be summarized using frequencies and percentages. OS will be estimated by the Kaplan-Meier (KM) method to obtain median estimates with two-sided 95% confidence intervals (CIs). OS may be assessed by line of therapy (LOT) and type of treatment received in each LOT, pending feasibility. Subgroup analyses will be conducted in both Cohort 1 and 2: • Unresectable locally advanced DDLPS patients • Metastatic DDLPS patients • Brightline-1-like cohort including patients who received doxorubicin monotherapy or doxorubicin-based regimens as 1L treatment. • Real-world Brightline-1 cohort including patients matching the inclusion and exclusion criteria in Brightline-1 trial • Additional subgroups pending feasibility, which may include age, sex, and year of diagnosis. Sensitivity analyses will be conducted: • to only include patients in areas covered by the National Mortality
	Database and with higher completeness on survival data • to only include patients before COVID-19 emergence (cohort identification period: January 1, 2013 – December 31, 2019) to assess the possible impact of COVID-19 pandemic on treatment patterns and outcomes
Milestones:	 Protocol approval: May 2023 Start of analysis: Dec 2023 End of analysis: Feb 2024 Final report of study results: Apr 2024

5. AMENDMENTS AND UPDATES

NIS Protocol BI Study Number 1403-0024 Page 10 of 37 C42272174

NIS Protocol BI Study Number 1403-0024 Page 11 of 37 C42272174

Proprietary confidential information© 2023 Boehringer Ingelheim GmbH or one or more of its affiliated companies

6. MILESTONES

Milestone	Planned Date
IRB/IEC approval	October 2023
Start of data collection	December 2023
End of data analysis	February 2024
Final report of study results:	April 2024

7. RATIONALE AND BACKGROUND

Liposarcoma is a malignancy of fat tissue and is one of the most commonly occurring types of soft tissue sarcoma, a heterogeneous group of rare malignancies with over 150 different histological subtypes. Liposarcomas have several forms based on clinical presentation, severity, genetic abnormality, and preferred treatment regimens [R23-1186] [R22-3794]. In 2020, the World Health Organization, reclassified liposarcomas into the following distinct categories: atypical lipomatous tumor/well-differentiated liposarcoma; myxoid liposarcoma; pleomorphic liposarcoma; myxoid pleomorphic liposarcoma; and dedifferentiated liposarcoma (DDLPS), which represents 15-20% of all liposarcoma cases [R23-1182].

DDLPS is characterized by amplification of the mouse double minute 2 homolog (MDM2) gene. MDM2 is a negative regulator of tumor protein 53 (TP53) [P20-03237]. There are few published epidemiological studies of DDLPS with quite limited incidence and prevalence data. According to an internal BI analysis of Surveillance, Epidemiology, and End Results (SEER) registry-21, the age-adjusted incidence rate of DDLPS is 0.18 per 10,000 person-years. Incidence is higher in men than women (0.26 per 10,000 py vs 0.11 per 10,000 py) (data on file).

DDLPS is typically a high-grade tumor that metastasizes in more than 20% of cases (lungs, liver, bone, skin, or brain). The mainstay of first line (1L) therapy for advanced DDLPS remains an anthracycline-based regimen despite its moderate efficacy in this setting (objective response rate <15%; median progression-free survival: 2 to 4 months; median overall survival (OS, from initiation of 1L treatment to death or end of study): 8 to 12 months) [R21-0720]. Notably, the natural history, patient journey and treatment outcomes of this rare disease is poorly understood in Chinese patients.

Boehringer Ingelheim (BI) is currently developing BI 907828, an orally available MDM2-p53 antagonist, for treatment of DDLPS. On 22 August 2022, BI China received Clinical Trial Notification (CTN) for MDM2 DDLPS indication from China authority. In the CTN, China authority recommended BI to collect Chinese DDLPS patients' survival and other related clinical data in the real-world, to provide support for future analysis during New Drug Application. Therefore, we conduct this study to investigate the patient characteristics, current treatment patterns and outcomes in Chinese DDLPS patients.

8. RESEARCH QUESTION AND OBJECTIVES

Primary objective:

To describe the overall survival of Chinese unresectable locally advanced or metastatic DDLPS patients

Secondary objectives:

To describe the treatment patterns of Chinese DDLPS patients

Exploratory objective:

To describe demographic, clinical characteristics and treatment outcomes of Chinese DDLPS patients To describe the direct medical cost and healthcare resource utilization of Chinese DDLPS patients

9. RESEARCH METHODS

9.1. STUDY DESIGN

This will be a non-interventional/observational study of Chinese DDLPS patients using existing data curated by . No Boehringer Ingelheim (BI) product will be studied, and no new interventions or procedures will be performed.

The primary outcome is overall survival (OS). Secondary outcomes include survival after initial diagnosis, and treatment patterns. Exploratory outcomes may include patient demographics, clinical characteristics, duration of treatment, time to next treatment by lines, healthcare resource utilization and direct medical cost, etc. None of the outcomes reflect safety issues.

9.2. SETTING

9.2.1. Study sites

This is a non-interventional study based on existing data. Details of data source are described in Section 9.9.4.

9.2.2. Study population

Inclusion criteria:

- Patient has two or more documented clinical visits in the National Anti-Tumor Drug Surveillance System (NATDSS) network on or after January 1, 2013.
- Patient has a confirmed diagnosis of DDLPS during his/her lifetime.
- At least 18 years old at the date of initial diagnosis

No exclusion criteria are applied.

Eligible population will be divided into two groups:

NIS Protocol BI Study Number 1403-0024

Page 13 of 37 C42272174

Proprietary confidential information© 2023 Boehringer Ingelheim GmbH or one or more of its affiliated companies

- Cohort 1 will include unresectable locally advanced or metastatic DDLPS patients who received at least one line of systemic antineoplastic treatment by the end of cohort identification period (index date = start date of 1L treatment).
- Cohort 2 will include patients with DDLPS who have not initiated 1L systemic antineoplastic treatment by the end of cohort identification period (index date = date of initial DDLPS diagnosis during cohort identification period). Patients initiated 1L treatment afterwards or patients received adjuvant and/or neoadjuvant therapy only through follow-up will be included in Cohort 2.

In both cohorts, 1L therapy will be defined as the initial set of drugs used after unresectable locally advanced or metastatic diagnosis. Metastatic patients will be defined as those with metastatic diagnosis or presence of metastatic sites; unresectable locally advanced patients will be defined as those with advanced diagnosis and without subsequent surgical resection.

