9.2.3. Study visits

Definitions of relevant time periods are detailed below.

Study period: January 1, 2013 – December 31, 2022

Baseline period: All available data prior to index date

[figure not shown]
Cohort identification period: January 1, 2013 – December 31, 2021 (one year before end of study period)

Index date: The index date for Cohort 1 will set to the date of initiation of 1L treatment; the index date for Cohort 2 will be the date of initial DDLPS diagnosis during cohort identification period.

Follow-up period: From index date until date of death, if available, or the date of censoring if there is no record of death, whichever occurs first. For survival and treatment patterns, the date of censoring will be the last activity date, defined as the date of the last visit of any type prior to the end of the study period.

Figure 1 illustrates the time periods for the study timelines.

(a). Cohort 1

NIS Protocol BI Study Number 1403-0024

Page 14 of 37 C42272174

Proprietary confidential information© 2023 Boehringer Ingelheim GmbH or one or more of its affiliated companies (b). Cohort 2

[figure not shown]

Figure 1. Overall study period

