9.5. STUDY SIZE

The patient sample was a convenience population of all eligible patients in the database who met inclusion and exclusion criteria during the study period; no priori power analyses were conducted.

NIS Protocol BI Study Number 1403-0024 Page 22 of 37 C42272174

Proprietary confidential information© 2023 Boehringer Ingelheim GmbH or one or more of its affiliated companies

A preliminary feasibility check will be conducted to assess potential eligible sample size as below.

Criteria
Patients with at least one diagnosis of DDLPS
Patients aged 18 years old or above at initial diagnosis
Patients have two or more documented clinical visits between January 1, 2013 and December 31, 2022

We estimated the precision we can expect from the estimates of a median OS for different potential sample sizes. It is assumed that the enrollment rates follow uniform distribution in the study period and that the survival time follows exponential distribution with median OS=8, 10, and 12 months. The censor rate is approximately 20% with type I of right censoring. The 95% CI of median OS is shown in the below table under different scenarios.

N (Sample Size)	Median Overall Survival from start of 1L, Months	95% CI of Median Overall Survival
1500	8	(7.419, 8.625)
1000	8	(7.287, 8.764)
500	8	(7.011, 9.095)
300	8	(6.732, 9.435)
1500	10	(9.262, 10.784)
1000	10	(9.100, 10.972)
500	10	(8.754, 11.378)
300	10	(8.408, 11.814)
1500	12	(11.110, 12.948)
1000	12	(10.916, 13.175)
500	12	(10.491, 13.677)
300	12	(10.073, 14.198)

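### The two-visit inclusion rule is not tied to the index date, so some patients must survive to a second visit to be counted; this shifts the Kaplan-Meier curves up, probably only slightly for primary OS

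*Protocol*

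**What the plan says.** The inclusion criterion in Protocol 9.2.2, repeated in SAP 6.3, is "Patient has two or more documented clinical visits" in the NATDSS network, dated 1 January 2013 or later. No other exclusions apply. The feasibility table in Protocol 9.5 puts an end date on the window: "Patients have two or more documented clinical visits between January 1, 2013 and December 31, 2022". That is a year after cohort identification closes on 31 December 2021.

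Time zero is set separately in Protocol 9.2.3: "The index date for Cohort 1 will set to the date of initiation of 1L treatment", and "the index date for Cohort 2 will be the date of initial DDLPS diagnosis during cohort identification period". Survival after initial diagnosis, a secondary outcome in both cohorts, is counted from diagnosis.

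Deaths for OS come from the linked national mortality database (SAP 10.1.1), whether or not the patient is still attending. Patients without a death record are censored at the last activity date, "defined as the date of the last visit of any type prior to the end of the study period".

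The visible analysis sections (Protocol 9.7.1, 9.7.2 and 9.7.5; SAP 10.1) give no landmark, delayed entry or sensitivity analysis for this rule. The limitations in Protocol 9.9 cover 80% death capture, missing and coded data, generalisability and COVID-19. They do not mention survival to a second visit, although the ENCePP checklist item that gives time-related bias as an example refers to that section.

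**The concern.** A criterion that can be met after time zero uses future information to decide who is counted from time zero. Between the index date and the second visit, an affected patient cannot die and still be in the analysis.

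The loss is not balanced between deaths and censored times. Take a patient whose only network visit is at time zero. With no death record, the patient is censored on day 0 and adds nothing to the Kaplan-Meier estimate, so exclusion changes nothing. With a linked death, the patient would have contributed an event, and the rule removes it.

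The outputs at stake are the primary OS median and the 6-, 12-, 18- and 24-month survival rates, which Protocol section 12 says may supplement regulatory submissions. Unlike sampling error, the shift does not shrink as the cohort grows.

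**Working it through.** **1. The plan's own precision figures.** Protocol 9.5 assumes exponential survival with a median of 8, 10 or 12 months and about 20% censoring. The log-log 95% limits for the median are the times t at which |ln(λt) − ln(ln 2)| = 1.96·√V(t)/(λt). Here λ = ln 2/m and V(t) = (1/N)∫₀ᵗ λe^(λu)/G(u) du, with G the censoring survival function. With uniform entry giving 20% censoring and m = 10:
- N = 1500: 9.252 to 10.776 (Protocol 9.262 to 10.784)
- N = 300: 8.362 to 11.779 (Protocol 8.408 to 11.814)

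All 12 rows agree within 0.7%. The Protocol's half-widths at m = 10 are (10.784 − 9.262)/2 = 0.76 months and (11.814 − 8.408)/2 = 1.70 months. They are the yardstick below.

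**2. Inputs not in the documents (assumed).** s is the share of patients whose second visit falls after time zero. g is the gap to that visit. The calculation assumes complete follow-up and that every surviving patient returns.

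**3. Fixed gap.** The fraction removed is f = s(1 − 2^(−g/m)). All removed deaths precede the median, so the new median is m[1 − log₂(1 − f)]. With m = 10 and g = 21 days = 0.69 months, 1 − 2^(−0.069) = 0.0467:

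| s | f | Median (months) | Change |
|---|---|---|---|
| 10% | 0.0047 | 10.07 | +0.7% |
| 25% | 0.0117 | 10.17 | +1.7% |
| 50% | 0.0233 | 10.34 | +3.4% |
| 100% | 0.0467 | 10.69 | +6.9% |

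Simulations of the 10% case gave shifts of 0.03 to 0.07 months.

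**4. Longer, variable gap.** With an exponential gap of mean g, the chance of dying before the second visit is q = λ/(λ + 1/g). The included patients follow S(t) = [2^(−t/m) − s·q·e^(−(λ+1/g)t)]/(1 − s·q).
- Cohort 1, m = 10, g = 3 months: q = 0.0693/(0.0693 + 0.3333) = 0.172. With s = 25%, s·q = 0.043 and S(t) = 0.5 at t = 10.62, a rise of 6.2%.
- Survival after diagnosis, assumed m = 36, g = 1 or 3 months: q = 0.019 or 0.055. With s = 50% the median rises by 1.4% or 4.0%, and with s = 100% by 2.7% or 8.1%. At s = 100%, 6-month survival is 91% or 94%, against 2^(−6/36) = 89%.

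**5. Does delayed entry remove it?** Simulating m = 10 with exponential gaps, entry at the second visit brought the median back to within 1% of 10. It does not help if every patient's second visit comes at the same interval g. Nobody is then at risk before g, the curve estimates S(t)/S(g), and the median is m + g: 10 + 0.69 = 10.69 for three weeks and 12 for two months, with or without delayed entry.

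**The case against.** The strongest reply is that primary OS is barely touched. Cohort 1 starts at 1L, and "1L therapy will be defined as the initial set of drugs used after unresectable locally advanced or metastatic diagnosis", so many patients may have both a diagnostic and a treatment visit by the index date. A shift of 0.07 months at a 10% share is small beside a planned half-width of 0.76 to 1.70 months. This stands. The 36-month median and the larger shares are likewise assumptions and establish no size for Cohort 2.

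A reader might also infer three stronger things that the documents do not support.

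- **That the rule removes only early deaths.** Linkage finds deaths at any time, so a one-visit patient who leaves the network and dies much later is also removed. In simulations with 2% or 5% of patients leaving after each visit (assumed rates), about 28% or 49% of the removed recorded deaths came after the second visit would have been due. That part is selection on leaving care, not immortal time.
- **That the reported survival will exceed true survival.** The upward shift is relative to the same analysis without the rule. Counting linked deaths at any time while censoring survivors at their last visit pulls the curve down. With full death capture and patients leaving the network, a true 36-month median was estimated at 26.5 to 33.1 without the rule and 26.7 to 35.0 with it. The 80% death capture conceded in Protocol 9.9 pushes the other way.
- **That delayed entry always repairs it.** Step 5 of the working shows where it cannot.

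Finally, the public SAP text goes from 10.1.2 to 10.3, and Figure 1 is not shown, so a provision could sit in text not visible here. Protocol 9.7.5 is visible and lists two sensitivity analyses, neither of which concerns this rule.

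**Conclusion.** The point holds as a minor one. The visit rule is not anchored to the index date, it can be met by later visits, and relative to no such rule it moves Kaplan-Meier survival up whenever some patients lack two network visits by time zero. Where all patients have them, it has no effect.

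For primary OS the shift is probably under 2% of the median (shares of 10% to 25%, three-week gap). It reaches about 6% only with a 25% share and a three-month mean gap, when the 0.62-month rise approaches the half-width planned for N = 1500. Survival after diagnosis and Cohort 2 probably have more patients affected, because time zero is then the diagnosis itself. Every size rests on an assumed share, gap and exponential survival. The effect is separate from those of incomplete death capture and last-visit censoring, which may push the estimate in either direction.

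**What to change.** Keep the inclusion criterion. In the Kaplan-Meier analyses of OS and of survival after initial diagnosis, start each patient's time at risk at the later of time zero and the second qualifying visit.

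Tabulate the numbers at risk over the first months. If the early risk sets are empty or very small, as when nearly all second visits follow time zero at a similar interval, delayed entry cannot recover early survival. In that case also report a sensitivity analysis without the two-visit rule. That analysis is a complement and not the reference: with patients leaving the network and full death capture, dropping the rule gave a median of 9.7 to 9.9 against a true 10.

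Report how many patients the rule excluded and how many of them had a linked death. This would show directly whether the issue matters.

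The cost is one derived date, an entry-time option in the survival code and one line in the patient-flow table. The downside is smaller early risk sets and slightly wider early confidence intervals. Where both visits precede time zero, nothing changes.

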9.7.3. Analysis of exploratory objectives

Patient demographic, clinical characteristics and treatment outcomes will be reported for Cohort 1 and Cohort 2 (See Section 9.3.1.3 for variable definitions). If multiple records for a variable exist during the baseline period, the record closest to index will be chosen. The number of missing values will be reported for each variable, and percentages for categorical variables will be based on non-missing values. Time from diagnosis to 1L treatment, time to next treatment and duration of treatment by LOT will be estimated using KM methods to obtain median estimates with 95% CIs and IQRs.

HCRU including number of visits and days of hospitalization will be summarized as counts (n) and proportions (%). Direct medical cost will be summarized using mean, median and IQR.

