6.3 STUDY POPULATION

Inclusion criteria:

- Patient has two or more documented clinical visits in the National Anti-Tumor Drug Surveillance System (NATDSS) network on or after January 1, 2013.
- Patient has a confirmed diagnosis of DDLPS during his/her lifetime.
- At least 18 years old at the date of initial diagnosis

No exclusion criteria are applied.

Eligible population will be divided into two groups:

- Cohort 1 will include unresectable locally advanced or metastatic DDLPS patients who received at least one line of systemic antineoplastic treatment by the end of cohort identification period (index date = start date of first line (1L) treatment).
- Cohort 2 will include patients with DDLPS who have not initiated 1L systemic antineoplastic treatment by the end of cohort identification period (index date = date of initial DDLPS diagnosis during cohort identification period). Patients initiated 1L treatment afterwards or patients received adjuvant and/or neoadjuvant therapy only through follow-up will be included in Cohort 2.

In both cohorts, 1L therapy will be defined as the initial set of drugs used after unresectable locally advanced or metastatic diagnosis. Metastatic patients will be defined as those with metastatic diagnosis or presence of metastatic sites; unresectable locally advanced patients will be defined as those with advanced diagnosis and without subsequent surgical resection.

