10.1 MAIN ANALYSIS

10.1.1 Analysis of primary objective

OS will be analyzed for Cohort 1. For OS calculation, the event time is the date of death recorded by the National Mortality Database from CDC. OS is defined as the time from initiation of 1L until the date of death due to any cause. Patients without death record during the study period will be censored at the last medical record during the study period.

OS will be estimated by the KM method to obtain median estimates with 95% CIs and IQRs for Cohort 1, calculated using the log-log transformation. OS rate at 6, 12, 18, and 24 months will be described according to the survival curves if reached.

OS may be assessed by LOT and type of treatment received in each LOT, pending feasibility. OS by LOT is defined as the time from initiation of each LOT until the date of death due to any cause.

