10.1.2 Analysis of secondary objectives

Survival after initial diagnosis will be estimated by the KM method to obtain median estimates with 95% CIs and IORs for Cohort 1 and Cohort 2.

Treatment patterns for Cohort 1 and Cohort 2 will be described by the number of lines, count with percentage (%) of patients by treatment lines, type of therapy and therapy regimens in each line.

LOTs are defined by the temporal relationship and sequencing of treatment regimens by using the dates of initiation and discontinuation of chemotherapy, targeted therapy, and/or immunotherapy. For each patient, 1L treatment regimen is defined as the first systemic treatment of any chemotherapy, and/or targeted drugs given to a patient after advanced or metastatic DDLPS diagnosis. A treatment line is advanced to the next line when a patient initiates new combinations of drugs or has the evidence of progression of disease. The start date of each LOT is defined as the date of initiation of new regimen, and the end date of each LOT is defined as the date of last dose prescribed or recorded at/before discontinuation.

Statistical and Epidemiological Analysis Plan (SEAP) for Observational and Non-Interventional Studies (ONIS)

Page 18 of 36

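### Two different 1L anchors, and a DDLPS diagnosis accepted at any date, leave the Cohort 1 index date for primary OS open; under one anchor, patients confirmed after 1L add guaranteed survival time

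*Protocol*

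**What the plan says.** Protocol 9.2.2 and SAP 6.3 share the diagnostic criterion: "Patient has a confirmed diagnosis of DDLPS during his/her lifetime". Protocol 9.2.2 adds "No exclusion criteria are applied", and the feasibility check in Protocol 9.5 counts "Patients with at least one diagnosis of DDLPS". None of these sets an order between DDLPS confirmation and treatment.

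The time origin depends on 1L. Protocol 9.2.3 states "The index date for Cohort 1 will set to the date of initiation of 1L treatment", and SAP 10.1.1 states "OS is defined as the time from initiation of 1L until the date of death due to any cause". SAP 10.1.1 does not itself define 1L. Two other places do:

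- SAP 6.3 (same wording in Protocol 9.2.2): "1L therapy will be defined as the initial set of drugs used after unresectable locally advanced or metastatic diagnosis". The diagnosis is not stated to be DDLPS.
- SAP 10.1.2, under the secondary objectives: the first systemic treatment "given to a patient after advanced or metastatic DDLPS diagnosis". Here it is.

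**The concern.** Take a hypothetical patient treated in 2015 for metastatic liposarcoma of another or unspecified type and confirmed as DDLPS on re-biopsy in 2018. Under Protocol 9.2.2 and SAP 6.3 as worded, the patient can enter Cohort 1 with a 2015 index date. The patient is in the dataset only because of survival to 2018, so the first three years of follow-up could not have contained a death. A similar patient who died in 2016, before re-biopsy, is never selected. This is guarantee-time (immortal-time) bias.

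Under SAP 10.1.2 read literally, the 2015 treatment is not 1L. The first regimen after 2018 takes that label, or, if none follows, the patient has no 1L and leaves Cohort 1. The guaranteed time disappears, but a later-line regimen may be tabulated as 1L. That would affect the treatment-pattern tables and the subgroup defined by doxorubicin as 1L (Protocol 9.7.4).

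Two programmers following the documents could therefore produce different primary index dates. Protocol 7 says the study answers a regulator's recommendation to collect survival data, and Protocol 12 says it may supplement submissions.

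**Working it through.** **Inputs from the documents.** Exponential survival with a median of 8, 10 or 12 months, about 20% censoring and the precision table (Protocol 9.5); Kaplan-Meier with log-log intervals (Protocol 9.7.1); OS counted from 1L start (SAP 10.1.1).

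**Inputs not in the documents, so assumed.** The share f of Cohort 1 confirmed after 1L, and the delay D from 1L to confirmation. After confirmation the hazard is taken to equal everyone else's.

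**1. The plan's own precision figures.** For an exponential median m, the limits are m × exp(±1.96 × √(I/N) / ln 2). I is the Greenwood integral at the median: 1.086 for uniform censoring that gives 20% censored. For m = 10 and N = 1500 the exponent is 1.96 × √(1.086/1500) / 0.693 = 0.076, which gives (9.27, 10.79) against the stated (9.262, 10.784). Across all 12 rows the interval widths agree within -0.8% to +1.5%. The table is a sound yardstick.

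**2. Fixed delay.** With S(t) = 2^(-t/m), the observed curve is

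S_obs(t) = (1-f) × S(t) + f × min(1, S(t)/S(D)).

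When the observed median exceeds D, setting S_obs = 0.5 gives t = m × log2{2 × [(1-f) + f × 2^(D/m)]}. For m = 10, f = 10%, D = 6: 10 × log2{2 × [0.9 + 0.1 × 1.516]} = 10.73 months.

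| Observed median, true median 10 | f = 5% | f = 10% | f = 20% |
|---|---|---|---|
| D = 3 months | 10.17 | 10.33 | 10.65 |
| D = 6 months | 10.37 | 10.73 | 11.42 |
| D = 12 months | 10.78 | 11.70 | 13.33 |

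**3. Spread of delays.** For D uniform between two bounds among late-confirmed patients, S(t)/S(D) is averaged over D and the median solved numerically, again with true median 10.

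| Delay, months | f = 5% | f = 10% | f = 20% |
|---|---|---|---|
| 0-3 | 10.08 | 10.16 | 10.32 |
| 1-6 | 10.20 | 10.40 | 10.79 |
| 1-12 | 10.42 | 10.84 | 11.65 |
| 1-24 | 10.60 | 11.25 | 12.69 |

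The last row needs caution: its mean delay, (1+24)/2 = 12.5 months, exceeds the assumed median OS.

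**4. Against the plan's precision.** The share f that moves the median to the stated upper 95% limit at N = 1500, for true medians of 8, 10 and 12 months:

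- D = 3: 18.7%, 24.2%, 29.7%
- D = 6: 8.2%, 10.8%, 13.6%
- D = 12: 5.0%, 5.0%, 5.6%

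At N = 300 and D = 6 the shares are 19.4%, 26.0% and 32.7%.

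**5. Direction.** Let the post-confirmation hazard be 2.5 times higher, with m = 10, f = 10%, D = 6. At t = 10 the curve is 0.9 × 0.5 + 0.1 × 2^(-2.5 × 4/10) = 0.45 + 0.05 = 0.50, so the median is back at 10. Worse survival after confirmation can cancel the rise.

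**6. Do the remedies work?** A simulation used 60,000 source patients, true median 10, 20% of them confirmed late, exponential delays with mean 6 months, and those who died before confirmation removed. Late-confirmed patients made up 15.0% of the resulting cohort. The uncorrected median was 10.81. Restriction to confirmation on or before 1L gave 10.10, delayed entry at confirmation 10.09, and indexing at the later date 10.09.

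**The case against.** The strongest reply is that the plan already means DDLPS throughout. The Cohort 1 sentence speaks of advanced or metastatic DDLPS patients, so the diagnosis named in the next paragraph is naturally the same one. SAP 10.1.2, the only readable section with rules for starting, advancing and ending a line, says so explicitly. On that reading, time before confirmation is not counted and the calculation above does not apply. This stands in part: the upward bias belongs to one reading and is not an established property of the plan. But SAP 10.1.2 can also be read as dating advanced disease in anyone ever labelled DDLPS. Read literally, it brings the relabelling problem instead. It does not settle the matter.

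A reader might infer from the Histology row of SAP mock Table 2, which has an Other category, that the plan expects patients with another histology at index. The documents do not support this. A blank shell row states no expectation, and the variable definitions that might explain it are blacked out. The rule that "the record closest to index will be chosen" does not show it either.

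A reader might also infer that OS is certain to be materially overestimated. Neither f nor D is given. If late confirmation is mostly late filing of a pathology report, delays are short and the effect is 0.1-0.3 month. Worse survival after confirmation could offset it.

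Finally, parts of the SAP between 10.1.2 and 10.3 cannot be read, so a relevant analysis there cannot be ruled out. What can be said is that the two sensitivity analyses in Protocol 9.7.5 (mortality-data completeness and COVID-19) do not address this, and that Protocol 9.9 names a different source of overestimation, incomplete death capture.

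**Conclusion.** The point holds as an inconsistency that affects the primary time origin. Two stated 1L anchors, combined with a diagnosis accepted at any date, can give different Cohort 1 index dates for the same patient. One admits guaranteed survival time into OS; the other, read literally, may mislabel a later regimen as 1L.

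The size cannot be fixed from the documents. At a true median of 10 months with equal hazard after confirmation, it is under 0.2 month for a late share of 5% and a 3-month delay. It reaches 0.7 month at 10% and 6 months. At N = 1500 and a 6-month delay, late shares of about 8% to 14% carry the median to the protocol's own upper confidence limit. The change is worth making before the dataset is locked; it does not show that the planned estimate is wrong.

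**What to change.** - Use one 1L definition, in the same words, in Protocol 9.2.2, SAP 6.3 and SAP 10.1.2.
- For the primary OS analysis, require that the first confirmed DDLPS diagnosis is dated on or before 1L start. Do not re-index later regimens as 1L.
- Report how many patients were confirmed after 1L start, with the distribution of the delay.
- Add a sensitivity analysis that includes these patients, preferably with delayed entry (left truncation) at the confirmation date. This keeps the 1L time origin without counting guaranteed time. It assumes that, once confirmed, they have the same hazard as others at the same time since 1L. Adding them back without delayed entry would return late-filed reports and true reclassifications together, with the guaranteed time included.

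Indexing at the later of the two dates also removes the guaranteed time, but it changes what OS is measured from.

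The cost is one clause in each document, one count and one sensitivity table. The downside is that the primary estimate loses the late-confirmed patients, including those whose pathology report was only filed late; the delayed-entry analysis shows how much that matters.
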